Valacyclovir is the oral L-valyl ester prodrug of acyclovir and is converted to acyclovir via first-pass hepatic metabolism. Valacyclovir's properties have been reviewed.^{15,16} Valacyclovir is approved by the United States Food and Drug Administration (FDA) for the treatment of herpes zoster and genital herpes and for the suppression of herpes virus infections including HSV-1.¹⁷ Acyclovir is phosphorylated by viral thymidine kinases to its active form. This form inhibits DNA synthesis through competitive inhibition of viral DNA polymerase. Maximum plasma concentration of acyclovir is achieved in 1-3 hours after oral administration and the elimination half-life is 2.5-3.6 hours. Acyclovir is predominantly eliminated by glomerular filtration and tubular secretion. Valacyclovir is widely prescribed and considered to be relatively safe and well tolerated.¹⁷

Risks and Discomforts Associated with valacyclovir:

In clinical trials in adult patients, adverse events commonly observed more frequently with valacyclovir than placebo and at a rate of $\geq 10\%$ are:

- Headache
- Nausea
- Stomach pain

In clinical trials in adult patients, adverse events observed more frequently with valacyclovir than placebo and occurring at a rate of $<10\%$ but $>1\%$ are:

- Dizziness
- Painful periods (females only)
- Joint pain
- Depression
- Vomiting
- Fatigue (sleepiness)
- Rash
- Low blood cell counts (neutrophil and platelet)
- Inflammation of the nose and throat
- Upper respiratory tract infection
- Increased liver enzyme levels (signs of liver damage)

The following are rare but are considered serious adverse reactions:

- **Thrombotic Thrombocytopenic Purpura/Hemolytic Uremic Syndrome (TTP/HUS):** This is a blood clotting problem which can be fatal. Cases of TTP/HUS, in some cases resulting in death, have been reported in patients who have advanced HIV disease and in patients who have had transplants and are on valacyclovir
- **Acute Renal Failure (kidney failure):** cases have been reported in elderly patients, those with underlying kidney disease, patients taking other drugs that may cause damage to the kidneys, and patients without adequate hydration (dehydrated)
- **Central Nervous System Effects:** agitation, hallucinations, confusion, delirium, seizures, and encephalopathy (brain swelling) have been reported in adult patients who received higher-than-recommended doses of valacyclovir¹⁷

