The recommended dosage for suppression of recurrent genital herpes is 500-1000 mg taken once daily. Safety and efficacy of this regimen have been established for patients receiving these doses for up to 1 year. In a large-scale, 1 year, dose finding study for valacyclovir use in genital herpes suppression, 5.1% of all patients enrolled had discontinued their therapy because of an adverse event.¹⁸ The percentages for discontinuing therapy were similarly distributed among the 6 treatment groups of the study (4 valacyclovir groups at 250 mg, 500 mg, 1 g once daily, or 250

mg twice daily; 1 acyclovir group at 400 mg twice daily; and 1 placebo group).¹⁸ Valacyclovir adverse events reported in this study include headache, rhinitis, infection, flu-like syndrome, pharyngitis, nausea, back pain, diarrhea, abdominal pain, sinusitis, and dyspepsia. The frequency of these adverse events to valacyclovir was similar to that observed in patients receiving placebo. Abnormal laboratory tests for anemia, leukopenia, thrombocytopenia, AST (SGOT), and serum creatinine were also evaluated and the frequency of adverse events to valacyclovir was similar to that observed in patients given placebo and no association was observed between valacyclovir treatment and any abnormal laboratory test.¹⁸ Doses up to 8 grams per day were used in pre marketing studies.¹⁷ The study medication dose for this study will be 1.5 g by mouth, twice daily. This dose is identical to the University of Pittsburgh pilot trial (see below) and it is adequate for suppressive HSV-1 therapy.¹⁷ We are proposing to use the dose of 1.5 g twice daily because this was the dose shown to be effective in the Prasad study.

Pilot trial of valacyclovir augmentation in early course schizophrenia

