3.0 Specific Aims

The Primary Aim of the Study is:

1. To determine the efficacy of adjunctive valacyclovir, in comparison to placebo, to improve visual (Brief Visuospatial Memory Test) and working (composite score of the Spatial Span and Letter Number Span tests) memory in individuals who are HSV-1 positive and early in the course of schizophrenia. We hypothesize that individuals who are HSV-1 positive, but not those who are HSV-1 negative, will demonstrate significant valacyclovir efficacy for visual and working memory.

The Secondary Aims of the Study are:

1. To evaluate the efficacy of adjunctive valacyclovir, in comparison to placebo, to improve general cognitive performance as measured by the MATRICS composite score in HSV-1 positive and negative subjects.
2. To evaluate the efficacy of adjunctive valacyclovir, in comparison to placebo, to improve functional performance and quality of life as measured by the USCD Performance-Based Skills Assessment, Version B (UPSA-B), Quality of Life Enjoyment and Satisfaction Questionnaire – Short Form (Q-LES-Q-SF) and Personal and Social Performance Scale (PSP) and to improve global functional assessments as measured Clinical Global

Impressions Severity Scale (CGI-S) and Clinical Global Impressions Severity Improvement scale (CGI-I) scores in HSV-1 positive and negative subjects.

3. To evaluate the efficacy of adjunctive valacyclovir, in comparison to placebo, for general and positive symptoms as measured by the PANSS total and Marder subscale factor scores and negative symptoms as measured by the NSA-16 in HSV-1 positive and negative subjects.
4. To evaluate the tolerability and safety of valacyclovir treatment in this population.
5. To explore changes in the levels of inflammatory markers - HSV2, CMV, EBV, CRP, and Toxoplasmosis – and their relationship to treatment outcomes.

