9.0 Safety Assessments and Procedures

The investigator is responsible for appropriate medical care of subjects during the study. The investigator remains responsible for the following, through an appropriate health care option, adverse events that are serious or that caused the subject to discontinue before completing the study. The subject should be followed until the event is resolved or explained. Frequency of follow-up evaluation is left to the discretion of the investigator.

Vital Signs: Vital signs will be assessed at study visits per Study Procedures Table (Attachment 1). Vital signs include: body weight, height (Visit 1 only), blood pressure, heart rate, waist circumference (optional per study site), and temperature (optional per study site). Blood pressure and heart rate will be taken in a seated position or supine position after a rest period of five minutes.

Medical History: The subject's lifetime medical history will be taken during the screening period. Medical history includes previous and current diseases.

Physical Examination: A physical examination including a neurological examination and an assessment for active infections, including orolabial lesions.

Electrocardiograph (ECG): A supine, 12 lead ECG will be performed according to the Study Procedures Table (Attachment 1). Potentially clinically significant ECG abnormalities will be interpreted by a local cardiologist at the discretion of the investigator and/or medical designee.

Suicidality: Suicide-related events will be assessed and evaluated at every visit through a clinical interview by a trained clinician designated by the site PI.

*Any abnormal findings and severity, causality or sequelae will be documented. Clinically significant changes in vital sign measurements, ECGs, labs, or findings during physical examination (including orolabial lesions) and findings during the clinical interview from baseline will be documented as adverse events and causality will be assessed.

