12.0 Study Medication/Treatment

Valacyclovir hydrochloride and matching placebo capsules will be used as study medication for this study. Placebo capsules will look like valacyclovir capsules, with matching shape, taste, and color. Subjects will be instructed to take 6 capsules of study medication daily.

The investigator or his/her designee is responsible for explaining the correct use of the study medication to the subjects, verifying subject understanding and agreement, maintaining accurate records of dispensing and collection, and destroying all unused medication according to their pharmacy standard operating procedures at the end of the study. Subjects will be instructed to contact the investigator as soon as possible if they have a complaint or problem with the study medication so that the situation can be assessed.

Method of Assignment to Treatment

Subjects who meet all criteria for enrollment will be 1:1 randomized in a double-blind fashion to adjunctive treatment with valacyclovir or placebo at Visit 2. Assignment to treatment groups will be determined by a computer-generated random sequence provided to sites by an unblinded biostatistics team at Indiana University. To minimize potential imbalance among treatment groups of factors that may influence efficacy outcomes, a stratified random assignment of subjects to therapy will be used to insure equal representation of HSV1 positive and negative subjects in the placebo and valacyclovir arms. The stratification factors used for this study include the investigative site.

Compounding and Pharmacy Oversight

Study medications will be sent to study sites at regular intervals from the University of Iowa which is contracted by Indiana University for preparation and shipping study medication for this study.

Study medication will be purchased directly through Indiana University. University of Iowa pharmacy will over-encapsulate the valacyclovir and create matching placebo capsules. Study medication will be stored according to the details on the product label (59° to 77° F).

Dosing

The dosing used in this study is 3 capsules of either valacyclovir or /placebo by mouth twice per day, given without regard to meals. Each valacyclovir capsule will contain 500 mg of active ingredient for a total daily dose of 3 grams per day. Dose reductions of 2 capsules per day will be permitted to address adverse events at the discretion of the site investigator.

Dispensing

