For PANSS scores, which are assessed at 4 post-baseline visits, we will also use mixed model ANCOVA with a similar set of fixed effects, but will compare the fit of linear or higher order polynomials to estimate time trends in treatment effects. In past studies in schizophrenia using the CGI, we have observed that 1) most values are clustered tightly among 3 or 4 of the 7 possible grades of severity, and 2) few subjects change more than 1 or 2 points. These features that suggest linear mixed models may be inappropriate for detecting change in the CGI. Accordingly, we will assess change in the CGI as follows: 1) For each subject, we will compute the Spearman rank correlation between visit number and CGI score for all visits observed, as a nonparametric measure of trend; and, 2) a Wilcoxon test will be used to compare the average magnitude of within-participant Spearman trend scores a) between all participants on Valacyclovir and Placebo; b) between participants on are HSV-1 seropositive and on valacyclovir or placebo; or, c) between participants on are HSV-1 sero negative and on valacyclovir or placebo. We will use multiple imputation of missing CGI data to assess the sensitivity of these analyses to missing data.

Another analysis objective is to assess the safety and tolerability of valacyclovir treatment in this patient population. Safety data will be analyzed using incidence density analysis to compare the rates of adverse events (AEs) across groups. Incidence density analysis is ideal for adverse events comparisons, because event frequencies are adjusted for the total duration of follow-up, and thus corrects for different rates of follow-up between study groups. The occurrence of all adverse events will be compared, as will the occurrence of the following categories of adverse events: total AEs, serious AEs, psychiatric AEs, and AEs grouped by organ system. Survival analysis techniques will also be employed to compare retention time across groups. In addition, secondary analyses will include testing for drug versus placebo effects in all participants without consideration of HSV-1 sero status. All statistical analyses will be conducted using SAS 9.1.

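### Laboratory values matching the drug's named harms are collected at three visits, but the safety analysis plans no comparison of those values between arms

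*Combined protocol and SAP*

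**What the plan says.** Secondary Aim 4 in Section 3.0 is "To evaluate the tolerability and safety of valacyclovir treatment in this population". Among the drug's risks, Section 2.0 lists "Low blood cell counts (neutrophil and platelet") and "Increased liver enzyme levels (signs of liver damage"), both in the band between 1% and 10% and more frequent than on placebo. It lists "Acute Renal Failure (kidney failure") as rare but serious.

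Section 11.0 and Attachment 1 collect a blood count with differential, a metabolic panel and creatinine clearance at Visit 1 (screening), Visit 6 (Day 56) and Visit 10 (Day 112).

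For the analysis, Section 16.0 states: "Safety data will be analyzed using incidence density analysis to compare the rates of adverse events (AEs) across groups". Events are compared in total and for serious, psychiatric and organ-system groups. The same paragraph adds a survival comparison of retention time.

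The link from laboratory result to adverse event is in Section 9.0, which has "Clinically significant changes in vital sign measurements, ECGs, labs, or findings during physical examination (including orolabial lesions") documented as adverse events. That section gives no numeric grading. Section 10.0 does set numeric limits, for discontinuation: transaminases, hemoglobin, white cells, serum creatinine and creatinine clearance.

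On dose, Section 12.0 gives 500 mg capsules "for a total daily dose of 3 grams per day". The laboratory reassurance in Section 2.0, that "no association was observed between valacyclovir treatment and any abnormal laboratory test", comes from a suppression study whose largest valacyclovir dose was 1 g/day.

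**The concern.** The trial measures the quantities through which the named harms would first show, and then has no stated plan to compare them. A moderate fall in creatinine clearance or platelets on active drug, not large enough for a site to record as an event or to cross a discontinuation limit, would appear in no planned result. The aim could then be reported as showing no difference in adverse event rates while the measured values differed by arm.

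The dose makes this more relevant. The only laboratory evidence summarised in the protocol comes from a third of the study dose or less (1 g against 3 g per day). Leaving laboratory summaries unspecified also leaves the choice of parameters, time points and cut-offs until after the data are seen.

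**Working it through.** The plan states no rate, power or sample size for safety, so there is no figure to reproduce. The check is mainly a comparison of sections.

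**Step 1: named harm, measurement, planned analysis**

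| Harm (Section 2.0) | Measured at Visits 1, 6, 10 | Section 10.0 limit | Planned comparison of values by arm |
|---|---|---|---|
| Low neutrophils | Blood count with differential | None (total white cells only, <1500) | None |
| Low platelets | Blood count | None | None |
| Raised liver enzymes | Metabolic panel | Transaminases >3 × ULN | None |
| Acute renal failure | Metabolic panel, creatinine clearance | Creatinine >1.5; clearance <50 ml/min | None |

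That the metabolic panel supplies creatinine and transaminases is an inference, but the Section 10.0 limits could not be applied without them. The protocol does not itself tie each test to each harm.

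**Step 2: routes by which a laboratory change can reach the analysis**

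1. A site judges it clinically significant and records an adverse event. It then enters the rates, possibly under an organ-system group.
2. It crosses a Section 10.0 limit and the subject is discontinued. It then shortens retention time, but retention is not split by cause, and no count of subjects crossing a limit is planned.

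A change that takes neither route is not compared. Section 15.0 does not close the gap: for the site safety boards' periodic review it names enrollment and adverse event counts, not laboratory values.

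**Step 3: illustration only, on assumed inputs**

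The 175 subjects randomized 1:1 give about 87 per arm (175 / 2 = 87.5). At two-sided 5% and 80% power, the detectable shift in a continuous value is (1.960 + 0.842) × √(2/87) = 0.425 SD. The t-test power at 0.43 SD is 0.805. With 60 per arm tested it falls to 0.65.

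The table sets a comparison of means against a count of subjects beyond a cut-off. It assumes 87 per arm, a normally distributed value, a cut-off that 2% of placebo subjects exceed, and Fisher's exact test for the count.

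| Assumed drug effect | Beyond cut-off, drug v placebo | Power, means | Power, counts |
|---|---|---|---|
| All subjects shift 0.43 SD | 5.2% v 2.0% | 0.81 | 0.08 |
| 5% of subjects shift 3 SD | 6.0% v 2.0% | 0.14 | 0.13 |
| 10% of subjects shift 3 SD | 10.1% v 2.0% | 0.38 | 0.51 |

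For the uniform shift, placebo tail rates of 1% and 5% give count power of 0.02 and 0.24. The ordering depends on the pattern of effect, which the documents do not settle. This supports reporting both the values and the threshold counts. It does not measure the loss under the current plan.

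**The case against.** The strongest reply is that the plan is less bare than it looks. Section 10.0 sets numeric limits, so extreme values do not rest on site judgement alone, and discontinuations feed the retention comparison. Organ-system grouping can separate renal, hepatic and blood events. Section 9.0 also requires abnormal findings to be documented. All of this stands, so a reader should not infer that laboratory harms would go unreported, or that only site-judged events count. What remains is that neutrophils and platelets have no limit, retention mixes all causes, and changes short of a recorded event or a limit are not compared.

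A reader might also infer that dividing by follow-up time biases the comparison, because subjects leaving before Visit 6 may have no post-dose test. The documents do not support that. Such subjects contribute under 56 of 112 days, and if early departure is similar by arm, both rates are diluted alike. Nothing in the documents suggests that it differs.

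A third tempting reading is that the dose is untested. Section 2.0 mentions pre-marketing doses up to 8 g/day, and a 24-subject pilot that reached 3 g/day and was well tolerated. It gives no laboratory results for either, so these statements do not replace this trial's own data, but they rule out any claim that there is no experience at the dose.

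Finally, the plan is silent on laboratory tables; it does not exclude them. The sponsor may produce them anyway. The point is that nothing commits to them or fixes their content in advance.

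**Conclusion.** The point holds as a gap in the stated safety analysis. Four named harms have matching laboratory measurements at one screening and two post-dose visits, and no section plans a summary, shift table, threshold count or between-arm comparison of the values. Followed as written, Secondary Aim 4 would be answered at 3 g/day from adverse event rates and retention alone.

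Its size cannot be derived from the documents. The contrast of 0.81 with 0.08 invites the inference that the current plan forfeits most of its power. That rests on a uniform 0.43 SD shift, chosen because it gives about 80% power, and on complete laboratory follow-up. The advantage disappears or reverses if only 5% to 10% of subjects react. Nor is there any implication that the drug is unsafe at this dose. This is a cheap improvement to a secondary aim and does not touch the primary endpoints.

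**What to change.** Add the following to the safety paragraph of Section 16.0:

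- **Values.** For creatinine, creatinine clearance, ALT/AST, neutrophils and platelets, summarise by arm the value and the change from screening at Visits 6 and 10. Give between-arm estimates with two-sided confidence intervals from the repeated-measures model already specified in that section, with the screening value as the baseline covariate.
- **Worst post-dose value.** Summarise by arm each subject's most abnormal result, including unscheduled, repeat and discontinuation tests, so that subjects withdrawn for abnormal values are not lost from view. Section 11.0 already provides for repeat tests, and Section 10.0 leaves discontinuation assessments to the investigator.
- **Existing limits.** Tabulate by arm the subjects crossing each Section 10.0 limit at any post-dose test.
- **Neutrophils and platelets.** As these have no Section 10.0 limit, give shift tables against the laboratory reference range.
- **Denominator.** For the counts and shift tables, use subjects with at least one post-dose test, and state how many in each arm had none.

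No discontinuation rule or visit schedule changes. The cost is SAP wording and a few tables from data already collected. The downside is more safety comparisons, so the text should say that they are read as estimates and not as hypothesis tests.

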17.0 Privacy/Confidentiality Issues

Confidentiality will be protected by ensuring all research staff have been properly trained in confidentiality and human subject research procedures, coding all subject information when possible, and by securing subject files in a locked filing cabinet or on secured databases with access available only to the investigator and research staff. Furthermore, data entered into a computer database will only use subject codes on secured computers that will be password protected with access available only to the investigator and research staff. Any screening information obtained from potential research subjects who subsequently do not participate in the research study will be destroyed.

18.0 Record Retention

Paper copies of medical records and source documentation will be kept for at least seven years after the study is closed with the IRB. One year after study closure, the documents may be shipped site specific long-term storage facility until destruction.


ATTACHMENT 1

Study Procedures Table

	Screening Period	Baseline								Termination
	Visit 1	Visit 2 ^a	Visit 3	Visit 4	Visit 5	Visit 6	Visit 7	Visit 8	Visit 9	Visit 10
Day		0	14	28	42	56	70	84	98	112
Visit Window Intervals			12-16 days	12-16 days	12-16 days	12-16 days	12-16 days	12-16 days	12-16 days	12-16 days
(in days)	0-30 days	N/A	(+/- 2 days)	(+/- 2 days)	(+/- 2 days)	(+/- 2 days)	(+/- 2 days)	(+/- 2 days)	(+/- 2 days)	(+/- 2 days)
Informed Consent	X									
Demographics, Substance/ Medical/Psychiatric History, review of current and previous medications	X									
SCID	X									
Physical Exam	X									X
Health Resource Utilization		X				X				X
Habits ^d	X	X	X	X	X	X	X	X	X	X
ECG (triplicate 1 min apart)	X									
Vitals	X	X				X				X
Labs (CMP ^b , CBC w/ diff)	X					X				X
TSH	X									X
Hepatitis Panel	X									
Uric Acid	X									X
Lipid Panel	X									X
HgbA1c	X									X
Creatinine Clearance	X					X				X
HSV1	X									
Urinalysis	X					X				X
Urine pregnancy test	X	X				X				X
Urine toxicology	X	X				X				X
Inflammatory markers	X									X
Repository ^c	X									
CGI-I			X	X	X	X	X	X	X	X
CGI-S and Suicidality clinical interview	X	X	X	X	X	X	X	X	X	X
PSP & Q-LES-Q-SF		X				X				X
MATRICES & UPSA-B		X				X				X
NSA-16		X		X		X		X		X
PANSS		X		X		X		X		X
Adverse Events		X	X	X	X	X	X	X	X	X
Concomitant Meds	X	X	X	X	X	X	X	X	X	X
Medication Dispensation		X	X	X	X	X	X	X	X	
Medication Accountability			X	X	X	X	X	X	X	X

^aNote: Visit 2 procedures may be split over 2 visits at the site discretion. Assessments should be no more than 7 days apart if split visit occurs.

^bNote: Calcium level is included in the CMP panel.

^cOptional. Consent must be obtained for participation in repository

^dBaseline/Lifetime Habits is collected at the screening visit

ATTACHMENT 2

Concomitant Medication Table

Medication	Use approved in study
Alpha 2 agonists (eg., Clonidine)	Stable dose, no changes or additions
Aminoglycoside antibiotics (systemic)	No
Anticholinergics	Conditional ^a
Antidepressants	Stable dose, no changes or additions
Antiemetics (eg., metoclopramide, domperidone, other dopamine receptor blockers)	Stable dose, no changes or additions Conditional ^b
Antiepileptic mood stabilizers (Divalproex, Oxcarbazepine, Lamotrigine, or Carbamazepine) & Lithium	Stable dose, no changes or additions ^g
Antiepileptics, non-mood stabilizers	Stable dose, no changes or additions EXCEPT topiramate not allowed
Antifungals (systemic)	No
Antineoplastics	No
Antipsychotic medications	Conditional ^c
Antivirals (including trantadine)	No
Barbiturates	Conditional ^b
Benzodiazepines & related sedatives (eg. Zolpidem)	Conditional ^a
Bisphosphonates	No
Contraceptives	Stable regimen ^g
Creatine	No
Cyproheptadine	Conditional ^b
Decongestants (eg., pseudophedrine)	Conditional ^c
Dextromethorphan	Conditional ^b
Dicyclomine	No
Herbal medications or Over the Counter Medications w/ primary CNS activity	No EXCEPT fish oil is acceptable
H2-Blockers (cimetidine, probenecid, and ranitidine) ^f	No ^f
Interferons	No
Hydroxyzine	Conditional ^b
Immunoglobulins	No
Immunosuppressants (DMARDs) (systemic)	No
Live attenuated vaccine	Caution ^d
Midrin	Conditional ^b
Minocycline	No
Muscle relaxants	Stable dose, no changes or additions Conditional ^b

(continues)

Concomitant Medication Table (continued)

Opiates/Opioids	Stable dose, no changes or additions Conditional ^b
Other Psychotropics Not Mentioned Elsewhere	Stable dose, no changes or additions
Penicillamine	No
Pentamidine	No
Roflumilast	Stable dose, no changes or additions
Tramadol	Stable dose, no changes or additions Conditional ^b
Trazodone	Stable dose, no changes or additions Conditional ^b
Vancomycin	No

^aConditional. See section 13.0 of protocol

^bMay be used PRN but should be avoided 8 hours prior to cognitive testing. Record time and date of last administration prior to assessments.

^cStable dose prior to study for four weeks prior to randomization with no more than 50% change in dose from baseline over course of study. May be used PRN but should be avoided 8 hours prior to assessments.

^dCaution. Concomitant use of valacyclovir with live attenuated vaccinations can diminish the effectiveness of the vaccine. The CDC recommends stopping oral antiviral medication for 24 hours before the varicella zoster vaccine and for two weeks following vaccination.

^eConditional. Recommended for "as needed"/PRN use, no longer than 7 consecutive days and no administration 24 hours prior to cognitive testing. Participants may take an expectorant in lieu of a decongestant.

^fExclusionary H2 blockers include: cimetidine, probenecid, and ranitidine. Other H2 blockers are not explicitly exclusionary, but use caution when prescribed as all are renally excreted with a potential to interfere with renal excretion & increase acyclovir levels.

^gFor female patients on carbamazepine, oxcarbazepine, and lamotrigine, oral estrogen-containing contraceptives may not be effective (due to cytochrome p450 3A4 interactions).
